| Criteria for Evaluation: | 
Safety:
 
Safety and tolerability will be based on an assessment of AEs, physical examinations, vital signs, electrocardiograms (ECGs), clinical laboratory tests, ophthalmologic assessments, and concomitant medications.
 
The MTD will be defined as the dose BELOW that dose which causes DLTs in $\geq 33\%$ of patients.
 
Pharmacokinetics:
 
Serial blood (plasma) samples and complete urine will be collected over 24-hour periods starting after the first (Day 1) and fifth (Day 5) doses of CPX-POM during Cycle 1 to characterize single dose and steady-state plasma and urine PK of CPX-POM, ciclopirox (CPX), and ciclopirox glucuronide (CPX-G). If patients are unable or unwilling to attend the required 12 hours of clinic visitation required for steady-state PK sampling on Day 5 of Cycle 1, the steady-state PK sampling may be postponed to Day 5 of Cycle 2. Urine β-glucuronidase activity will be measured prior to and after 5 days of CPX-POM administration (i.e., on Days 1 and 5 of Cycle 1).
 
Pharmacodynamics:
 
Blood will be collected to characterize the effects of CPX-POM on circulating biomarkers of Wnt and Notch cell signaling pathways. Plasma and peripheral blood mononuclear cells (PBMCs) will be isolated from blood. Vascular
 |

endothelial growth factor (VEGF), interleukin (IL)-6, and IL-8 concentrations will be measured in plasma by enzyme-linked immunoassay (ELISA). Quantitative real-time polymerase chain reaction (qRT-PCR) will be used to characterize gene expression of circulating biomarkers of Wnt and Notch signaling pathways in PBMCs.

**Statistical
Methods:**

Safety:

Safety data will be presented in by-patient listings. Categorical safety endpoints will be summarized by frequency of events/abnormalities for each dose group and overall. Continuous safety endpoints will be summarized using descriptive statistics (number of subjects [n], mean, standard deviation, median, first quartile [Q1], third quartile [Q3], minimum, maximum) for each dose group and overall.

Pharmacokinetics:

Standard PK parameters will be derived from resultant plasma and urine drug and metabolite concentration-time data using non-parametric methods. PK parameters will be summarized using descriptive statistics.

Pharmacodynamics:

[figure not shown]

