4. STUDY DESIGN

4.1. Overall Design

This is a first-in-human, Phase 1, multicenter, open label, dose escalation study to evaluate the DLTs and MTD and to determine the recommended Phase 2 dose (RP2D) of CPX-POM administered IV in patients with any histologically- or cytologically-confirmed solid tumor type. Secondary objectives include characterization of the safety and PK profile of CPX-POM and identification of preliminary anti-tumor activity in this patient population. Biomarkers and their relationship to PK and other outcomes will be examined as an exploratory objective.

The study will initially employ an accelerated titration design, with a single patient enrolled in each cohort (i.e., Single-Patient Cohorts). The initial patient cohort will receive CPX-POM at a starting dose of 30 mg/m². Doses will be escalated in 100% increments (i.e., doubling), until a \geq Grade 2 toxicity (with the exception of alopecia), as determined according to the United States (US) National Cancer Institute (NCI) Common Terminology Criteria for Adverse Events (CTCAE), version 4.03, is encountered, at which point that cohort and all subsequent cohorts will follow a classical “3 + 3” dose escalation design (i.e., standard cohorts).

After each cohort is completed, a Safety Review Committee (SRC) comprised of the CRO Medical Monitor, Principal Investigator(s), and Sponsor representatives will meet to discuss the data and decide upon the next dose escalation. Doses in the standard cohorts will be escalated in 25 to 50% increments, based on SRC decision, until the MTD is reached. In addition, after completion of Cycle 1 for the first 4 to 6 patients, the SRC will review safety, PK, and PD data to determine if any changes to the dosing schedule are indicated.

Inpatient dose escalation will not be allowed in any patient at any time.

Each patient in a dose cohort must have received at least 80% of their CPX-POM doses, unless due to toxicity, during Cycle 1 with follow-up safety evaluations through Day 22 (or Cycle 2, Day 1, if continuing in the study) to be eligible for the assessment of DLT.

Patients may continue to receive cycles of CPX-POM until progression of disease, intolerable toxicity occurs, or another withdrawal criterion applies.

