Approximately 24 patients will be enrolled in the Single-Patient and Standard Dose Escalation Cohorts to establish the MTD. In addition to these estimated 24 patients, Expansion Cohort(s) may be enrolled after the MTD is reached to either explore different dosing schedules, increase the experience with a particular tumor type (e.g., muscle invasive

bladder cancer [MIBC]), or to examine the safety and anti-tumor activity of CPX-POM in combination with certain other anticancer agents.

All patients are to attend a Follow-up Visit 28 days (\pm 5 days) after the last study drug dose. No follow-up after completion of the Follow-up Visit is planned, with the exception of monitoring of ongoing treatment-emergent adverse events (AEs) until resolution or until the AE is clearly determined to be due to a patient's stable or chronic condition or intercurrent illness(es).

Dose escalation procedures will be conducted as shown in Table 2. For further details and example doses, see Section 4.2.

Table 2. Dose Escalation Procedures

| Accelerated Titration (Single-Patient Cohorts; n=1 each) | |
|---|---|
| No \geq Grade 2 AEs | 
 Continue evaluation of single-patient dose cohorts. Escalate by 100% to next dose level. |
| At least 1 \geq Grade 2 AE not meeting the definition of DLT | 
 Expand current and subsequent cohorts to at least 3 patients (see Standard Dose Escalation Scheme below). |
| 1 DLT | 
 Expand current cohort up to 6 patients or until 2 DLTs are encountered (Standard Dose Escalation Scheme below). |
| Standard Dose Escalation (Standard Cohorts; n=3 to 6 each) | |
| No DLT | 
 Escalate by 25–50% to next dose level. |
| 1 DLT in \leq 3 patients | 
 Expand cohort up to 6 patients. |
| 1 DLT in 6 patients | 
 Escalate by 25–50% to next dose level. |
| > 1 DLT in \leq 6 patients | 
 MTD reached; stop dose escalation. Possibly explore intermediate doses for the RP2D. |

Abbreviations: AE = adverse event; DLT = dose limiting toxicity; MTD = maximum tolerated dose; RP2D = recommended Phase 2 dose.

A Dose-Limiting Toxicity will be defined as any of the following, if deemed related to study drug:

- Grade 4 thrombocytopenia of any duration
- Grade 3 thrombocytopenia with significant hemorrhage of any duration

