9.2. Analysis Sets

9.2.1. Safety

The **Safety Set** will consist of all patients who receive at least 1 dose of study drug. All safety and PD data will be analyzed using the safety set.

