9.5.1. Determination of Maximum Tolerated Dose

The MTD is defined as the highest dose at which 1 or fewer of up to 6 patients experience a DLT. The MTD will be exceeded if 2 or more patients in a cohort of up to 6 patients experience a DLT. The number and proportion of patients who experience a DLT or Grade 2 or higher AE will be listed and summarized by dose group. A logistic regression will be used to estimate the predicted toxicity probability at each dose level. Details will be provided in the statistical analysis plan.

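### The protocol's DLT-evaluability rule reaches no supplied analysis set, and no supplied shell counts patients with any DLT or any Grade 2+ AE by dose

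*Protocol*

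**What the plan says.** **Eligibility for DLT assessment.** Protocol Section 4.1, repeated in the synopsis, requires that each cohort patient "must have received at least 80% of their CPX-POM doses, unless due to toxicity, during Cycle 1 with follow-up safety evaluations through Day 22". For patients who go on treatment, the follow-up ends at the first visit of the second cycle instead.

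**Analysis sets.** Section 9.2 defines a Safety Set (at least one dose) and a PK Set. Section 9.2.1 adds: "All safety and PD data will be analyzed using the safety set". SAP Table 14.1-2 lists Safety, Efficacy and PK populations.

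**MTD.** Section 9.5.1 uses counts: "The MTD is defined as the highest dose at which 1 or fewer of up to 6 patients experience a DLT". The synopsis uses a proportion: "The MTD will be defined as the dose BELOW that dose which causes DLTs in" at least 33% of patients.

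**Promised output.** Section 9.5.1: "The number and proportion of patients who experience a DLT or Grade 2 or higher AE will be listed and summarized by dose group". Then: "A logistic regression will be used to estimate the predicted toxicity probability at each dose level". Then: "Details will be provided in the statistical analysis plan".

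**Grading.** Section 8.2.1.7 has the investigator assign a CTCAE-based grade to every AE.

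**Shells.** Tables 14.3-1.7 and 14.3-1.8 have rows for Mild, Moderate and Severe. Listing 16.2.7-1 uses the same severity words and has no DLT column. Table 14.1-1 has a DLT row under reasons for discontinuing a cycle.

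The supplied SAP file contains table and listing shells only. A footnote to Listing 16.2.8-5 points to SAP text outside it.

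**The concern.** DLT counts and proportions by dose are the reported result for the primary objective. The protocol sets one rule for who can be assessed for a DLT and another for which patients enter safety analyses, and the two differ. A patient who stops early in Cycle 1 for progression or withdrawal, without toxicity, is outside the first and inside the second. Such a patient adds to the denominator but has not been observed long enough to show a DLT, so the reported proportion falls.

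The second problem is coverage. A programmer working from the supplied shells could not produce the summary and listing promised in Section 9.5.1. Nothing marks which patients had a DLT, and the AE severity scale is not the one on which AEs are graded.

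**Working it through.** **1. Is the evaluability rule in any set?** With five daily doses per cycle, 80% is 0.8 × 5 = 4 doses, matching the 4-of-5 wording in the Section 4.1 DLT definition.

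| Set | Condition | 80% / Day 22 rule? |
|---|---|---|
| Protocol Safety Set | at least one dose | no |
| Protocol PK Set | sample obtained and analysed | no |
| SAP Safety population | at least one dose | no |
| SAP Efficacy population | dosed, measurable disease, post-baseline tumour assessment | no |
| SAP PK population | sample obtained and analysed | no |

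The Cycle 1 completion flag in Table 14.1-1 cannot stand in for the rule: for patients who continue, it needs only the Day 10 visit.

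**2. Effect on the proportion.** With d DLTs among 6 evaluable patients, and k treated non-evaluable patients without a DLT, the Safety Set proportion is d/(6 + k). Assumptions: the cohort is filled to six evaluable patients, and k is 0 to 3. The documents give no value for k.

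| k | d = 2 | d = 1 |
|---|---|---|
| 0 | 2/6 = 33.3% | 1/6 = 16.7% |
| 1 | 2/7 = 28.6% | 1/7 = 14.3% |
| 2 | 2/8 = 25.0% | 1/8 = 12.5% |
| 3 | 2/9 = 22.2% | 1/9 = 11.1% |

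On six evaluable patients the synopsis proportion and the Section 9.5.1 count agree: two DLTs is at least 33%. On the Safety Set one non-evaluable patient is enough to make them disagree.

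The chance of at least one non-evaluable patient while reaching six evaluable is 1 − (1 − q)^6, where q is the non-evaluable rate. For assumed q of 5%, 10% and 20% this is 26%, 47% and 74%.

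**3. Do the shells give the promised counts?**

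- *Table 14.1-1*: DLT by dose, but only as a reason for discontinuing a cycle. Section 6.1.5 lets a patient restart after a DLT resolves, so that patient need not appear in the row.
- *Tables 14.3-1.1 to 14.3-1.6 and 14.3-1.9*: no DLT row and no grade.
- *Tables 14.3-1.7 and 14.3-1.8*: Mild, Moderate, Severe. If Mild meant Grade 1, Moderate plus Severe in the any-TEAE block of 14.3-1.7 would give Grade 2+, but no mapping is supplied. Grades 4 and 5 have no row of their own.
- *Table 14.3-2.1.4 and its replicates*: CTCAE grades by dose, one laboratory parameter at a time. These cannot be added into a count of patients.
- *Listing 16.2.7-1 and its replicates*: severity words, no DLT column.

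No supplied shell gives patients with any DLT by dose, or patients with any CTCAE Grade 2+ AE by dose. None presents the logistic regression.

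**4. The logistic regression.** Section 9.5.1 states no outcome, dose scale, population or estimator. Suppose the outcome is DLT and the fit is ordinary maximum likelihood. If no dose below the stopping dose has a DLT, the likelihood keeps rising as the slope grows: fitted risk tends to 0 at every lower dose and to the observed proportion at the stopping dose. The slope is then not finite and the fitted risk at the MTD is 0%. With 0/3 at that dose, the exact 95% upper limit is 1 − 0.025^(1/3) = 71%.

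**The case against.** **The detail may be in SAP text that was not supplied.** This is fair. Section 9.5.1 defers to the SAP, and Section 9 calls itself a summary. A DLT set and a model specification are what such text would contain, so their absence is claimed only for the supplied documents. The protocol does, however, state two rules that conflict, and SAP text would not by itself change shells that use a different severity scale and contain no DLT table.

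**A reader might infer that the wrong MTD could be declared.** The documents do not support this. Protocol Table 2, the synopsis escalation table and Section 9.5.1 all act on counts, and a non-evaluable patient does not change the number of DLTs. Only the reported proportions move. The shift from 33.3% to 28.6% is also small against the uncertainty: the exact 95% interval for 2/6 is 4% to 78%.

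**A reader might take the enrolled-patient percentages in Table 14.1-1 as a competing DLT rate.** They are not. It is an ordinary disposition table, and percentages of enrolled patients are usual there.

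**A reader might think Grade 3 and Grade 4 blood counts are merged in the Severe row and lost.** They are not lost: platelets and neutrophils are named parameters in Table 14.3-2.1.4, with separate rows for each grade, and Listing 16.2.8-1 shows the grade of each result. The gap is for AEs outside the laboratory tables.

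**A reader might infer that the logistic regression will fail.** That depends on an outcome and estimator the supplied documents do not state. The preceding sentence in Section 9.5.1 also names Grade 2+ AEs, so that outcome is a possible reading. Even with DLT as the outcome, failure is not general. With 0/1 at 30, 60 and 120, 0/3 at 240, 350 and 475, 1/6 at 600 and 2/6 at 750 mg/m² (24 patients), maximum likelihood on log dose is finite and gives 12% at 600 and 36% at 750. The model does not set the MTD.

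**Conclusion.** The point holds as a conflict between stated rules plus a gap in the supplied shells. Section 4.1 restricts who is assessable for a DLT, while Section 9.2.1 as written analyses DLTs in everyone dosed. One treated non-evaluable patient takes a reported 2/6 = 33.3% to 28.6%, below the synopsis limit; three take it to 22.2%. These figures assume that non-evaluable patients have no DLT and that cohorts are filled to six evaluable patients. How often this would happen cannot be derived from the documents.

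The promised summary and listing of any DLT and any Grade 2+ AE by dose cannot be built from the supplied shells. The consequence is for how the primary result is reported, not for dose decisions. The logistic regression point is limited to missing specification. The item should be fixed because it bears on the primary objective and costs little.

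**What to change.** 1. **Analysis set.** Define a DLT-Evaluable Set in the Section 4.1 wording. Use it for DLT proportions and for any dose-DLT model, and keep the Safety Set for the other AE tables. State that the synopsis proportion and the Section 9.5.1 counts refer to the same evaluable patients.
2. **Shells.** Use CTCAE Grades 1 to 5 in Tables 14.3-1.7 and 14.3-1.8 and Listing 16.2.7-1, and add a DLT column to the listing. Add one table by dose of patients with any DLT (DLT-Evaluable Set) and any Grade 2+ AE (Safety Set), with exact intervals for the DLT proportions.
3. **Logistic regression.** State the outcome, dose scale and population. Note that an ordinary maximum likelihood fit may not be finite if no dose below the stopping dose has a DLT. The choice of estimator can be left to the sponsor's statistician.

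If SAP text that was not supplied already covers (1) or (3), cite it in Section 9.5.1 and align the shells with it.

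**Cost:** protocol and SAP wording, a change of severity rows, one listing column and one table. Section 8.2.1.7 already requires a grade for every AE. The CRF was not supplied, so check that it captures both grade and DLT status. No dose or clinical rule changes.

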9.5.2. Extent of Exposure

Patients' extent of plasma and urine exposure to CPX-POM and metabolites will be summarized by dose group.

9.5.3. Adverse Events

Clinical and laboratory AEs will be coded using the Medical Dictionary for Regulatory Activities (MedDRA). System Organ Class (SOC), High-Level Group Term (HLGT), High-Level Term (HLT), Preferred Term, and Lower-Level Term (LLT) will be attached to the clinical database.

AEs will be summarized on the basis of the date of onset for the event. A treatment-emergent AE will be defined as any AE that begins on or after the date of first dose of CPX-POM.

Summaries (number and percentage of patients) of treatment-emergent AEs (by SOC, and Preferred Term) will be provided by dose group and overall:

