| Duration of Study: | Patients who receive one treatment cycle will be in this study for up to approximately 8 weeks: up to a 28-day Screening period, a 21-day Treatment cycle, and a Follow-up period out to 28 ± 5 -days after the last dose (i.e., approximately Day 33). After the first treatment cycle, patients may continue to receive cycles of CPX-POM until progression of disease, intolerable toxicity occurs, or another withdrawal criterion applies. |

| | |
|---|---|
| Diagnosis and Main Eligibility Criteria: | 
Patients eligible for enrollment in this study will be adults with any histologically- or cytologically-confirmed metastatic or advanced-stage solid tumor that is refractory to standard therapy. Patients should only be included if no therapy exists or if they have received all standard therapies that would be potentially curative or might provide significant benefit. Patients must have a life expectancy ≥ 3 months, an Eastern Cooperative Oncology Group (ECOG) Performance Status 0 or 1, no significant ischemic heart disease, adequate hepatic function, and a baseline glomerular filtration rate (GFR) > 50 mL/min/1.73m². Females must not be pregnant and, if of childbearing potential, must use an effective method of contraception to avoid pregnancy during and for 3 months after participation in the trial.
 
Patients who have any risk factor for torsade de pointes or any uncontrolled or severe intercurrent medical condition, or who have had major surgery or prior systemic chemotherapy or radiation therapy within the previous 4 weeks are excluded.
 |
| Test Product, Dose, and Mode of Administration: | 
Escalating doses of CPX-POM will be administered by 10-minute IV infusion once daily on Days 1-5 of each 21-day cycle.
 
After completion of Cycle 1 for the first 4 to 6 patients, the SRC will review safety, PK, and PD data to determine if any changes to the dosing schedule are indicated (e.g., adding an additional 5 days of dosing to each treatment cycle).
 
Patients may continue to receive cycles of CPX-POM until progression of disease, intolerable toxicity occurs, or another withdrawal criterion applies. The starting dose will be 30 mg/m².
 |
| Reference Therapy, Dose, and Mode of Administration: | 
Not applicable.
 |

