- Other situations. Medical or scientific judgment should be exercised in deciding whether SAE reporting is appropriate in other situations such as important medical events that may not be immediately life-threatening or result in death or hospitalization but may jeopardize the patient or may require medical or surgical intervention to prevent one of the other outcomes listed in the above definition. These events should usually be considered serious. Examples of important medical events include invasive or malignant cancers, intensive treatment in an emergency room or at home for allergic bronchospasm, blood dyscrasias or convulsions that do not result in hospitalization, or development of drug dependency or drug abuse.

8.2.1.2. Time Period and Frequency for Collecting Adverse Event and Serious Adverse Event Information

All AEs and SAEs will be collected from the signing of the informed consent form (ICF) through the Follow-up visit.

Medical occurrences that begin before the start of study intervention but after obtaining informed consent will be recorded on the Medical History/Current Medical Conditions section of the CRF not the AE section.

Investigators are not obligated to actively seek AE or SAE after conclusion of the study participation. However, if the investigator learns of any SAE, including a death, at any time after a patient has been discharged from the study, and he/she considers the event to be reasonably related to the study intervention or study participation, the investigator must promptly notify the Sponsor.

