Sponsor: CicloMed
Protocol: CPX-POM-001
Statistical Analysis Plan
(TFL shells):
Version 1.0 / 02FEB2018

Table 14.3-1.1 - Overview of Adverse Events
 (Safety Population)

	CPX-POM 30 mg/m ² N=1 n (%)	CPX-POM [D2] mg/m ² N=X n (%)	CPX-POM [D3] mg/m ² N=X n (%)	CPX-POM [D4] mg/m ² N=X n (%)	CPX-POM [D5] mg/m ² N=X n (%)	CPX-POM [D6] mg/m ² N=X n (%)	CPX-POM [D7] mg/m ² N=X n (%)
Number of patients with at least one:							
AE	XX (XX.X)	XX (XX.X)	XX (XX.X)	XX (XX.X)	XX (XX.X)	XX (XX.X)	XX (XX.X)
TEAE *	XX (XX.X)	XX (XX.X)	XX (XX.X)	XX (XX.X)	XX (XX.X)	XX (XX.X)	XX (XX.X)
Related TEAE	XX (XX.X)	XX (XX.X)	XX (XX.X)	XX (XX.X)	XX (XX.X)	XX (XX.X)	XX (XX.X)
TEAE leading to discontinuation	XX (XX.X)	XX (XX.X)	XX (XX.X)	XX (XX.X)	XX (XX.X)	XX (XX.X)	XX (XX.X)
Related TEAE leading to discontinuation	XX (XX.X)	XX (XX.X)	XX (XX.X)	XX (XX.X)	XX (XX.X)	XX (XX.X)	XX (XX.X)
Serious TEAE	XX (XX.X)	XX (XX.X)	XX (XX.X)	XX (XX.X)	XX (XX.X)	XX (XX.X)	XX (XX.X)
Serious related TEAE	XX (XX.X)	XX (XX.X)	XX (XX.X)	XX (XX.X)	XX (XX.X)	XX (XX.X)	XX (XX.X)

* A treatment-emergent adverse events (TEAE) is defined as an adverse event which started on or after the first dose of CPX-POM administration.
 MedDRA version <version number>.

Program: (Program name.sas) (run on: DDMMYYYY HH:MM)

Filename: (Specify file name.rtf)

PROGRAMMING NOTES:

- "Leading to discontinuation" is derived from action taken = permanently discontinued.
- **A last column with the header 'CPX-POM All Doses' will also be displayed.**

Table 14.3-1.2 - Number (%) of Patients with Treatment-Emergent Adverse Events by System Organ Class and Preferred Term (Safety Population)

System Organ Class/ Preferred Term	CPX-POM 30 mg/m ² N=1 n (%)	CPX-POM [D2] mg/m ² N=X n (%)	CPX-POM [D3] mg/m ² N=X n (%)	CPX-POM [D4] mg/m ² N=X n (%)	CPX-POM [D5] mg/m ² N=X n (%)	CPX-POM [D6] mg/m ² N=X n (%)	CPX-POM [D7] mg/m ² N=X n (%)
Number of patients with at least one TEAE	XX (XX.X)	XX (XX.X)	XX (XX.X)	XX (XX.X)	XX (XX.X)	XX (XX.X)	XX (XX.X)
System Organ Class #1	XX (XX.X)	XX (XX.X)	XX (XX.X)	XX (XX.X)	XX (XX.X)	XX (XX.X)	XX (XX.X)
Preferred Term #1	XX (XX.X)	XX (XX.X)	XX (XX.X)	XX (XX.X)	XX (XX.X)	XX (XX.X)	XX (XX.X)
Preferred Term #2	XX (XX.X)	XX (XX.X)	XX (XX.X)	XX (XX.X)	XX (XX.X)	XX (XX.X)	XX (XX.X)
Preferred Term #3	XX (XX.X)	XX (XX.X)	XX (XX.X)	XX (XX.X)	XX (XX.X)	XX (XX.X)	XX (XX.X)
<etc>							
System Organ Class #2	XX (XX.X)	XX (XX.X)	XX (XX.X)	XX (XX.X)	XX (XX.X)	XX (XX.X)	XX (XX.X)

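### By-dose adverse event percentages accumulate over unequal numbers of cycles, so they mix toxicity with time on treatment; a fixed early window shown alongside would separate the two

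*Protocol*

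**What the plan says.** Protocol 9.5.3 sets the display: "Summaries (number and percentage of patients) of treatment-emergent AEs (by SOC, and Preferred Term) will be provided by dose group and overall". The same section bounds the events only at the start: "A treatment-emergent AE will be defined as any AE that begins on or after the date of first dose of CPX-POM". The footnote to SAP Table 14.3-1.1 does likewise: "A treatment-emergent adverse events (TEAE) is defined as an adverse event which started on or after the first dose of CPX-POM administration".

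What closes the window in practice is the end of collection, in Protocol 8.2.1.2: "All AEs and SAEs will be collected from the signing of the informed consent form (ICF) through the Follow-up visit". Section 4.1 puts that visit 28 days (±5) after the last dose and leaves treatment length open: "Patients may continue to receive cycles of CPX-POM until progression of disease, intolerable toxicity occurs, or another withdrawal criterion applies".

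Section 9.5.1 adds a second by-dose summary: "The number and proportion of patients who experience a DLT or Grade 2 or higher AE will be listed and summarized by dose group". It states no window for the Grade 2 or higher count.

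SAP Tables 14.3-1.1 to 14.3-1.9 set the dose groups side by side, and the footnotes on repeated events count a patient once per term. Table 14.3-2.1.4 and its replicates (14.3-2.2.4 and 14.3-2.5.4) take each patient's worst grade on study. None of these shells is limited to Cycle 1 or split by cycle. DLT assessment, by contrast, is tied to Cycle 1 with follow-up to Day 22 or Cycle 2 Day 1 (Protocol 4.1). The SAP shells for disposition, laboratory summaries and vital signs are laid out by cycle or visit.

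**The concern.** A patient counted once per term can only move from unaffected to affected, so the percentage can only rise as treatment continues. Dose groups that stay on treatment for different lengths of time are then shown side by side as if their percentages meant the same thing. Each one combines the risk per cycle with the number of cycles given.

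The primary objective covers the dose recommended for further investigation as well as the MTD, and Protocol Table 2 allows intermediate doses to be explored for the recommended dose. Tolerability beyond the DLT count is therefore relevant. Groups hold 1 to 6 patients, so one long-staying patient who eventually has an event moves a column by between 1/6 = 16.7 and 1/1 = 100 percentage points.

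**Working it through.** **Inputs from the documents.** Dosing is "once daily on Days 1-5 of each 21-day cycle" (Synopsis). Follow-up is 28 (±5) days after the last dose (4.1). Cohorts hold 1 or 3 to 6 patients (Table 2). The documents give no event rate and no expected number of cycles, so every risk and duration below is an assumption.

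**Step 1: length of the window.** For k cycles on schedule, days from first dose to the nominal follow-up visit = 21(k − 1) + 5 + 28.
- k = 1: 0 + 5 + 28 = 33, which matches the approximate Day 33 in the Synopsis.
- k = 2: 21 + 33 = 54.
- k = 6: 105 + 33 = 138.

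**Step 2: one dose, different durations.** With a constant, independent risk p per cycle, the proportion affected is 1 − (1 − p)^k.
- p = 0.30: 30% at k = 1; 1 − 0.70^4 = 76% at k = 4.
- p = 0.15: 15% at k = 1; 1 − 0.85^4 = 47.8% at k = 4.

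**Step 3: two doses.** The expected order reverses when the ratio of cycles (lower dose to higher dose) exceeds ln(1 − pHigh)/ln(1 − pLow). For 15% against 30% that is ln 0.70/ln 0.85 = 2.19.

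| Risk per cycle, low / high | Cycles, low / high | Affected, low / high | Order |
|---|---|---|---|
| 15% / 30% | 2 / 2 | 27.8% / 51.0% | kept |
| 15% / 30% | 4 / 2 | 47.8% / 51.0% | kept, gap nearly gone |
| 15% / 30% | 5 / 2 | 55.6% / 51.0% | reversed |
| 15% / 30% | 6 / 2 | 62.3% / 51.0% | reversed |
| 10% / 40% | 6 / 2 | 46.9% / 64.0% | kept |
| 20% / 50% | 6 / 1 | 73.8% / 50.0% | reversed |
| 20% / 50% | 6 / 2 | 73.8% / 75.0% | kept |

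Break-even ratios for other assumed pairs are 1.60 (20% / 30%), 2.29 (20% / 40%), 3.39 (10% / 30%) and 4.85 (10% / 40%).

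**Step 4: risk that falls after Cycle 1.** Let the later risk be f × p, so the proportion affected is 1 − (1 − p)(1 − fp)^(k − 1). For 15% / 30% and 6 / 2 cycles:
- f = 0.75: 53.2% / 45.8%, reversed.
- f = 0.5: 42.4% / 40.5%, barely reversed.
- f = 0.25: 29.8% / 35.3%, kept.
- f = 0: 15% / 30%, kept.

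**Step 5: small cohorts.** This is the exact binomial probability that the lower dose shows the strictly higher percentage, for 15% / 30% per cycle. The all-cycle column uses 62.3% / 51.0% (6 / 2 cycles).

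| Patients per cohort | All cycles | Cycle 1 only |
|---|---|---|
| 6 and 6 | 54.5% | 15.7% |
| 3 and 3 | 45.4% | 16.0% |

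A common window removes the systematic part. About 16% remains from chance alone.

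**Step 6: is a Day 1 to 21 window covered by collection?** The earliest scheduled follow-up is 23 days after the last dose: Day 5 + 23 = Day 28 after five doses, and Day 1 + 23 = Day 24 after a single dose. Both lie beyond Day 21. Coverage falls short only for patients who die, are lost or terminate early before then.

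**The case against.** The summaries are descriptive, with no test or ranking between doses, and all-cycle counts are a conventional display. Escalation and the MTD rest on DLTs assessed on Cycle 1. The context needed to read the tables is partly there. Table 14.1-1 shows patients treated in each cycle by dose group, Table 14.1-7 shows exposure, and Listing 16.2.7-1 gives the onset day of every event, so a Cycle 1 count could be read off by hand. Only the table and listing shells of the SAP are available, and a main text could state a window.

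Most of this stands and limits the point. It does not remove it, because the planned percentages still have unequal windows. Exposure in Table 14.1-7 is never used as a denominator, and its days run from first to last dose, so off-drug days count (26 days for 10 doses in two cycles).

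A reader might infer more than the documents support:
- That these tables choose the dose. No section says so, and the MTD rule does not use them.
- That the order will reverse. The 20% / 50% example reverses at 6 / 1 cycles but not at 6 / 2, and scheduled response assessments come about every two cycles.
- That a dose which stops patients for toxicity hides that toxicity. A patient stopped for an adverse event is counted, and also appears in Table 14.3-1.6.
- That the logistic regression in 9.5.1 is distorted. That section does not say which toxicity it models.

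**Conclusion.** The point holds as a cheap improvement to the analysis plan. The by-dose percentages are cumulative incidences over windows that grow with time on treatment, and the Grade 2 or higher proportion in 9.5.1 has no stated window. Under the assumed constant risk, the same dose can read 30% or 76% according to whether patients stay one cycle or four.

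Reversal between doses is possible but conditional. In the pairs tried, the lower dose needs roughly 1.6 to 4.9 times as many cycles, and risk must persist after Cycle 1. The MTD is unaffected. What improves is the tolerability evidence by dose that sits beside it. All sizes rest on assumed risks and durations, independence between cycles, and equal cycle counts within a cohort.

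It might be tempting to treat the all-cycle tables as wrong or to demote them. The documents do not support that, because only those tables show late and cumulative toxicity.

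**What to change.** - In Protocol 9.5.3 and the SAP, add by-dose tables of patients with any, related, Grade 2 or higher, and Grade 3 or higher treatment-emergent events with onset on Days 1 to 21 from first dose. Use these for the by-dose reading.
- In 9.5.1, state the same window for the Grade 2 or higher proportion.
- Fix the window at Day 21 and do not extend it when Cycle 2 is delayed. A window ending at Cycle 2 Day 1 would be longer for patients whose next cycle is held for toxicity than for those who stop.
- Keep Tables 14.3-1.1 to 14.3-1.9 and Table 14.3-2.1.4 with its replicates as all-cycle tables, and head each dose column with the number of cycles started in that group.
- Base the grade cut-offs on the CTCAE grade that Protocol 8.2.1.7 has investigators assign. Table 14.3-1.7 shows only mild, moderate and severe.

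The cost is a few extra tables, produced by an onset-date filter on data already planned for collection. The downside is that toxicity starting after Day 21 appears only in the all-cycle set, so the two sets must be read together.
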